## **6. ANALYSES AND SUMMARIES**

### **6.1. Primary Endpoint**

#### **6.1.1. Assessment of Treatment Burden using Life Interference Total Score**

##### **6.1.1.1. Main Analysis**

Treatment burden will be assessed as the difference in mean Overall Life Interference total scores between the weekly injection schedule and daily injection schedule as assessed by the Patient Life Interference Questionnaire (as part of DCOA 1) completed by the Subject/Caregiver Dyad at baseline and after each treatment schedule experience. The analysis uses the available data from the assessments performed at the end of each treatment period (Week 12 and Week 24) and utilizes the FAS population for the primary analysis.

The primary endpoint is treated as a continuous variable and will be analyzed using the appropriate model from [Section 5.2.2](#). This model will be used to test the null hypothesis that the difference in Life Interference Total Score between weekly and daily regimens is zero versus the alternative that the difference is less than zero (weekly minus daily).

Descriptive summary of Overall Life Interference total score will be presented by each treatment period at baseline and at each post-baseline time point. Overall individual item scores will be descriptively summarized as well.

##### **6.1.1.2. Sensitivity Analyses**

To support the interpretation, the primary endpoint will be analyzed using the linear mixed effects model described in 6.1.1.1 but repeated using the PPS population as described in [Section 4](#).

To assess the impact of using an alternative method of capturing the responses to the DCOA 1, as opposed to the method described in Section 11.1.1 of the Protocol (questionnaires completed in person using an electronic device), the primary analysis will be repeated as a sensitivity analysis on the FAS excluding those questionnaires. Additionally, the same analysis will be repeated excluding only the questionnaires that were completed using an alternative method due to COVID-19, to assess the impact of the COVID-19 pandemic on the primary endpoint analysis.

### **6.2. Secondary Endpoint(s)**

All secondary endpoints will be analyzed as described in [Sections 5.2.1](#), [5.2.2](#), and [5.2.3](#) using the FAS population described in [Section 4](#). Descriptive summaries for each of the secondary endpoints in [Sections 6.2.1](#), [6.2.2](#), and [6.2.3](#) and the respective individual domains will be provided.

#### **6.2.1. Treatment Experience Assessed using DCOA 1 Questionnaire**

Treatment experience assessed as the difference in mean scores between the weekly injection schedule experience and daily injection schedule experience in each of the following

variables within DCOA 1 questionnaire completed at baseline and after subjects have experienced each treatment schedule:

- Pen ease of use,
- Ease of the injection schedule,
- Convenience of the injection schedule,
- Satisfaction with overall treatment experience,
- Willingness to continue injection schedule,
- Injection signs and symptoms (from the patient aged 8 years and above),
- Assessment of signs (from the caregiver for children <8 years old),
- Caregiver life interference, including family life interference,
- Missed injections.

These variables will be analysed and summarized in the same way as the primary endpoint ([Section 6.1.1.1](#)).

### **6.2.2. Treatment Experience Assessed using DCOA 2 Questionnaire**

Proportion of Subjects/Caregiver Dyads that select the weekly injection schedule compared to the daily injection schedule in each of the outcome domains below as assessed by the DCOA 2 Questionnaires completed at Week 24, using methods described in [Section 5.2.1](#) and [5.2.3](#):

- Choice of injection pen,
- Preferred injection schedule,
- Convenience of injection schedule,
- Easier to follow,
- Pen ease of use,
- Patient life interference,
- Caregiver life interference, including family life interference,
- Benefit relating to the injection schedule,

- Intention to comply.

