
 • Choice of injection pen. • Injection signs and symptoms (pain, bruising, stinging). • Caregiver report of signs (bleeding, bruising). • Missed injections. • To use a Patient Global Impression Severity-Impact on Daily Activities (PGIS-IDA) at baseline and at the end of each period (Week 12 and Week 24) to support the interpretation of scores from the Dyad Clinical Outcome Assessment (DCOA) 1 and DCOA 2 Questionnaires. 	
 • Assessment of Signs (from the Caregiver). • Caregiver Life Interference, including Family Life Interference. • Missed injections. • Proportion of Subject/Caregiver Dyads that select the weekly injection schedule compared to the daily injection schedule in each of the outcome domains below as assessed by the DCOA 2 Questionnaires completed at Week 24. 
 • Choice of injection pen. • Preferred injection schedule. • Convenience of injection schedule. • Easier to follow. • Ease of the injection schedule. • Patient life interference. • Caregiver Life Interference, including Family Life Interference. • Benefit relating to the injection schedule. • Intention to comply. • The Patient Global Impression at baseline and at the end of each period (Week 12 and Week 24).

Safety Objective:
	
Safety Endpoints:

 • To describe the safety and tolerability of somatrogon. 	
 • Frequency, severity, and relationship of adverse events to somatrogon. • Serious adverse events. • Discontinuations due to adverse events. • Frequency and severity of abnormal lab values. • Detection of anti-rhGH antibodies (and neutralizing antibodies). • Detection of anti-somatrogon antibodies (and neutralizing antibodies).

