9.3. Analysis of Secondary Endpoints

The continuous secondary endpoints will be analyzed using a linear mixed effects model including sequence, period, and treatment as fixed effects, and subject within sequence and within-subject error as random effects.

Additional details of the secondary endpoints will be described in the statistical analysis plan.

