## **5.2. General Methods**

### **5.2.1. Analyses for Binary Endpoints**

Descriptive statistics of binary data will include the number of non-missing observations and frequencies of the observed endpoint as well as the observed proportions. When appropriate, a two-sided 95% CI for the corresponding proportion will be provided using the Wilson score method.

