### **5.2.3. Analyses for Categorical Endpoints**

Descriptive statistics will include the number of non-missing observations, frequencies and proportions for each category of interest. When appropriate, a two-sided binomial 95% CI for the proportion of a specific category will be provided using the Wilson score method.

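### The DCOA 2 endpoints compare weekly with daily choices, but the only planned interval is for a single proportion, so the comparison can be left without a measure of precision

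*SAP*

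**What the plan says.** Protocol section 2 lists as a secondary endpoint the "Proportion of Subject/Caregiver Dyads that select the weekly injection schedule compared to the daily injection schedule in each of the outcome domains below", taken from DCOA 2 at Week 24. SAP 6.2.2 repeats the comparison ("Proportion of Subjects/Caregiver Dyads that select the weekly injection schedule compared to the daily injection schedule") and sends it to the methods of SAP 5.2.1 and 5.2.3.

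- SAP 5.2.1 (binary): "When appropriate, a two-sided 95% CI for the corresponding proportion will be provided using the Wilson score method".
- SAP 5.2.3 (categorical): "Descriptive statistics will include the number of non-missing observations, frequencies and proportions for each category of interest". Again only when appropriate, "a two-sided binomial 95% CI for the proportion of a specific category will be provided using the Wilson score method".

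Protocol 9.3 describes a model for continuous secondary endpoints only and otherwise defers: "Additional details of the secondary endpoints will be described in the statistical analysis plan". The readable SAP gives no interval or test for weekly against daily, no analysis restricted to dyads who chose a schedule, and no rule for any other answer. It also names no reference value or hypothesis for DCOA 2.

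On the denominator, SAP 5 makes the population size in the table header the default for percentages. SAP 5.2.1 and 5.2.3 count available answers, and SAP 5.3 leaves missing outcomes out of the analysis. No section says which denominator applies to DCOA 2.

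**The concern.** The endpoint is a contrast between two shares from the same dyads. The planned interval describes one share. With two answers, the daily share is one minus the weekly share, so an interval for one gives the other. With a third answer that link breaks: equality of weekly and daily then lies below 50%, and the CI for the weekly share no longer carries the uncertainty of the contrast. Setting a weekly CI beside a daily CI does not repair this, because the two shares are negatively correlated.

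Missing answers can have the same effect. DCOA 2 is collected only at Week 24. Under Protocol 6.3.3.1.1, subjects who stop treatment in Period I skip the questionnaires at their later visit, yet they stay in the FAS. If the header population is the denominator, these dyads act as a third category even for a two-answer item.

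The study defines its benefit as better adherence and acceptance. Preferred schedule, choice of pen, benefit of the schedule and intention to comply appear as endpoints only in DCOA 2. DCOA 1 and PGIS-IDA receive a modelled weekly-daily comparison; the direct choice questionnaire does not.

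**Working it through.** **The plan's figures.** The documents give no sample size or precision for DCOA 2. The primary-endpoint figure does reproduce: SD of the difference = sqrt(2 × (1 − 0.3)) = 1.183, and a paired t-test for 0.45 at 90% power needs 75 subjects (power 0.902); 75 × 1.2 = 90. This point does not affect it. The examples assume 80 responding dyads, between 75 and 90.

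**Formulas.** Let W and D be the weekly and daily shares among n dyads, and z = 1.96.

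- Wilson CI for W: [W + z²/(2n) ± z × sqrt(W(1 − W)/n + z²/(4n²))] / (1 + z²/n).
- Difference from one multinomial sample: W − D ± z × SE, with SE = sqrt([W + D − (W − D)²]/n).

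**Third answer (assumed split 36 weekly, 20 daily, 24 neutral; n = 80).** W = 0.45, D = 0.25.

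- Wilson for W: centre 0.452, half-width 0.107, giving 34.6% to 55.9%. Wilson for D: 16.8% to 35.5%.
- Difference: SE = sqrt((0.45 + 0.25 − 0.04)/80) = sqrt(0.00825) = 0.0908. So +20 points, 95% CI 2.2 to 37.8.
- Among the 56 dyads choosing a schedule: 36/56 = 64.3%, Wilson 51.2% to 75.5%.

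The two Wilson CIs overlap, yet the CI for the difference excludes zero. Treating the shares as independent would also be wrong: SE = sqrt((0.45 × 0.55 + 0.25 × 0.75)/80) = 0.0737, which is too small.

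**Same pattern at n = 90 (assumed split 40/22/28).** Wilson for weekly 34.6% to 54.7%; difference +20 points, 3.4 to 36.6.

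**Two answers (54/36/0 of 90).** Wilson 49.7% to 69.5%; difference +20 points, −0.2 to 40.2. Both lead to the same reading, so nothing is lost.

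**Denominator alone (assumed 90 in the FAS, 80 answering, 50 weekly, 30 daily).**

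| Denominator | Wilson CI for weekly | Weekly minus daily (95% CI) |
|---|---|---|
| 80 who answered | 51.5% to 72.3% | +25.0 points (3.8 to 46.2) |
| 90 in the header | 45.3% to 65.4% | +22.2 points (3.3 to 41.2) |

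The Wilson CI moves from above 50% to spanning it. The interval for the difference excludes zero either way.

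**What the Wilson CI can still show.** If W > 0.5 then D ≤ 1 − W < 0.5, so W > D whatever the third share. In every split where the Wilson lower limit exceeds 50% (465 splits at n = 75, 666 at n = 90), the CI for the difference also excludes zero. The converse fails. With a true tie and an assumed 20% neutral share, simulation at n = 80 puts the Wilson CI wholly below 50% in 46% of trials.

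**Choice of interval for the difference.** The plain Wald form is poor when nearly everyone chooses one schedule. At n = 80, simulated coverage is 77% for true shares 97/1/2 and 89% for 95/2/3. Adding 1 to each of the weekly and daily counts and 2 to n brings coverage to 95-99% across the splits run. In the 36/20/24 example it gives 37, 21 and n = 82: +19.5 points, 1.8 to 37.2.

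**The case against.** The strongest reply is that these are descriptive summaries. SAP 5.2.1 and 5.2.3 give the Wilson CI only when appropriate, and even the primary p-value has no threshold to meet (SAP 5.1). A reader might infer that the Wilson CI is a test against 50%, and that the plan therefore loses power or would report a tie as rejection of the weekly schedule. The documents do not support this. They name no reference value, so 50% is only the benchmark a reader may bring, and the 46% above is the frequency of a possible misreading, not the error rate of a planned test.

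A reader might also infer that the preference question goes unanswered. That is too strong. SAP 5.2.3 reports each category of interest, two-answer items are covered, and a lower limit above 50% does establish weekly over daily. A large lead often gets there: with 20% neutral and n = 80, it does so in about 79% of trials for a 50-point lead and 96% for a 60-point lead.

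The third answer cannot be confirmed. The questionnaires, some item types in SAP section 3 and much of the SAP derivation appendix are redacted, and coding rules could sit there. Sending DCOA 2 to both the binary and the categorical method suggests that some item is not binary. It does not show a weekly/daily/neutral format. Finally, DCOA 1 does give modelled comparisons for convenience, ease, satisfaction, willingness to continue and caregiver life interference.

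All of this limits the point. It does not supply an interval for the comparison that the endpoint names.

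**Conclusion.** The point holds in a limited form. The endpoint is a weekly-daily comparison, and the only specified interval is for one proportion. For two-answer items with a responders-only denominator, the plan is adequate. For items with a third answer, or if the header population is the denominator, the precision of the comparison is missing. In the worked example, a CI of 34.6% to 55.9% for weekly stands where the relevant result is +20 points (about 2 to 38). The third-answer case rests on assumed answer options. The denominator case rests on readable text that does not settle the rule, with assumed counts. This is a worthwhile, low-cost improvement to secondary endpoints; it does not affect the primary analysis or the sample size.

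**What to change.** In SAP 6.2.2:

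1. State each item's answer options, and that the denominator is the dyads who answered that item.
2. For each item offering a weekly/daily choice, report both proportions and the within-dyad difference (weekly minus daily) with a descriptive 95% CI for two shares from one multinomial sample. Use a method that holds up for lopsided splits: a score interval, or the Wald form after adding 1 to the weekly and daily counts and 2 to n. Keep neutral answers in the denominator.
3. As a supplement, give the weekly share among dyads choosing a schedule, with a Wilson CI read against 50%.
4. Keep the existing Wilson CIs as description.

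Averaging the difference over the two randomised sequences is optional. If it is done with equal weights, it needs its own standard error, 0.5 × sqrt(v1/n1 + v2/n2), where v = W + D − (W − D)² within each sequence; the pooled formula does not match that estimate.

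Cost: a few lines of SAP text and one more interval per item, with no new data. The added interval is visibly wider: in the 36/20/24 example 35.6 points against 21.3, a ratio of 1.67.

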### 6.2.3. Patient Global Impression – Impact on Daily Activities (PGIS-IDA)

The PGIS-IDA at baseline and at the end of each period (Week 12 and Week 24) will be summarized descriptively and the overall comparison by treatment will be analyzed using methods described in [Section 5.2.2](#).

### 6.2.4. Safety Endpoints

The following safety endpoints will be summarized descriptively in each treated group using the Safety population as described in [Section 4](#).

- Frequency, severity, and relationship of adverse events to somatrogon;
- Serious adverse events;
- Discontinuations due to adverse events;
- Frequency and severity of abnormal lab values;
- Detection of anti-rhGH antibodies (and neutralizing antibodies);
- Detection of anti-somatrogon antibodies (and neutralizing antibodies).

### 6.3. Other Endpoints

Number of subjects satisfying or not satisfying the compliance threshold of  $\geq 80\%$  adherence to injections will be presented by each treatment period (Week 12 and Week 24) and overall by treatment. Additionally, adherence will be summarized descriptively as a continuous variable, where adherence is defined as

$$\left(1 - \frac{\text{number of missed doses}}{\text{total number of doses subjects were supposed to take}}\right) \times 100.$$

### 6.4. Subset Analyses

Additional analyses for the primary endpoint using the FAS population may be undertaken if adequate number of subjects are available for each analyses. The following sub-analyses on Life Interference may be considered exploratory for this purpose and support the evidence for the potential advantage of weekly somatrogon in comparison to daily administration of Genotropin® as it is expected to result in increased adherence and better acceptance of weekly dosing:

- Aged <8 years vs  $\geq 8$  years;
- Aged 3 – 11 vs 12 - <18 years;

- Caregiver injection vs self-injection;
- Burdened vs not burdened, defined by the response at baseline to the question “During the past 4 weeks, how often were you bothered by growth hormone injections?” (question 3 from Patient Life Interference Section I questionnaire), as follows:
  - Not burdened: subjects experiencing little to no burden (never, rarely);
  - Burdened: subjects experiencing at least moderate burden (sometimes, often, always).

## **6.5. Baseline and Other Summaries and Analyses**

The following summaries will utilize the Safety population as described in [Section 4](#) and therefore will not be noted in respective sections.

### **6.5.1. Baseline Summaries**

Descriptive statistics will be used to summarize the following variables:

- Age,
- Age groups (<8 vs  $\geq 8$  - <18),
- Sex,
- Ethnicity,
- Race,
- Region,
- Body weight,
- Body height,
- Body mass index.

### **6.5.2. Study Conduct and Participant Disposition**

The number of subjects screened and randomized will be summarized.

The number and percentage of subjects in each analysis set, completing the study and each disposition phase (period I, period II, follow-up) prematurely discontinuing the study by disposition phase, and the reason for subject discontinuation, will be summarized.

### 6.5.3. Study Treatment Exposure

Extent of exposure will be summarized. Descriptive statistics will be reported for the duration of treatment within each treatment period which is defined as:

- Genotropin: last dose date – first dose date + 1.
- Somatrogen: last dose date – first dose date + 7.

The number and percentage of subjects experiencing a dose reduction due to IGF-1 SDS >2 will be summarized.

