5.4.1. Dose Modifications

There are no planned dose modifications for somatrogon or Genotropin[®] in this study. Throughout the study, reported adverse events (AEs) that are drug related may lead to a dose adjustment at the discretion of the investigator and medical monitor. If the severity will be reported as “moderate”, the dose may be reduced by 25% and if the severity will be reported as “severe“, the next dose may be held and the following dose may be reduced by 50%. The Investigator and Study Medical Monitor will communicate to track and assess dose modifications.

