8.2.2. Abnormal Test Findings

Abnormal objective test findings should be recorded as AEs when any of the following conditions are met:

- Test result is associated with accompanying symptoms; and/or

- Test result requires additional diagnostic testing or medical/surgical intervention; and/or
- Test result leads to a change in study dosing (outside of any protocol-specified dose adjustments) or discontinuation from the study, significant additional concomitant drug treatment, or other therapy; and/or
- Test result is considered to be an AE by the investigator or sponsor.

Merely repeating an abnormal test, in the absence of any of the above conditions, does not constitute an AE. Any abnormal test result that is determined to be an error does not require recording as an AE.

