9.4. Safety Analysis

- Adverse events (Screening, Visits 1, 2, 3, 4, 5, 6, 7, and follow-up);
- Injection site reactions (Visits 1, 2, 3, 4, 5, 6, 7);
- Injection device complaints (Visits 1, 2, 3, 4, 5, 6, 7);
- Vital signs (Screening, Visits 1, 3, 4, 6, 7);
- Body weight (Screening, Visits 1 and 7);
- Physical exam (Screening, Visits 1, 3, 4, 6, 7);
- Urine pregnancy (if applicable) (Screening, Visits 1, 4, and 7);
- Routine clinical safety lab testing, IGF-I, IGF-I SDS, hemoglobin A1c, FT4 (Screening, Visits 4 and 7), somatrogon level (Screening, Visit 4² and Visit 7²), anti-somatrogon Ab (and neutralizing Ab) (Screening, Visit 4² and Visit 7²), and anti-rhGH Ab (and neutralizing Ab) (Screening, Visits 4 and 7).

Safety data will be tabulated and listed according to Pfizer's standard reporting algorithms.

² Only for subjects who have been on somatrogon for the previous 12 weeks of treatment.

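### The SAP's only named dose-reduction summary counts a reason that is not a dosing trigger in the protocol, and the AE-driven reductions and held doses that the protocol allows have no specified summary

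*SAP*

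**What the plan says.** **SAP 6.5.3 (Study Treatment Exposure)** says that extent of exposure will be summarized. It defines duration within each period from the first and last dose dates, adding 1 day for Genotropin and 7 days for somatrogon. It has one sentence on dose changes: "The number and percentage of subjects experiencing a dose reduction due to IGF-1 SDS >2 will be summarized".

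**Protocol 5.4.1 (Dose Modifications)** begins "There are no planned dose modifications for somatrogon or Genotropin[®] in this study". It then makes one allowance: "reported adverse events (AEs) that are drug related may lead to a dose adjustment at the discretion of the investigator and medical monitor". For a moderate event the dose may be reduced by 25%. For a severe event "the next dose may be held and the following dose may be reduced by 50" per cent. IGF-I is not mentioned.

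**The IGF-I SDS threshold of 2** appears in two places in the protocol: as inclusion criterion 3 in Section 4.1, and in Section 1.3, which notes that IGF-1 exceeded +2 SDS in one child in the completed Phase 2 study.

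**Timing of IGF-I** is given in Protocol 9.4: "Routine clinical safety lab testing, IGF-I, IGF-I SDS, hemoglobin A1c, FT4 (Screening, Visits 4 and 7". Protocol 6.2.4 and 6.2.7 agree.

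**Other SAP summaries that bear on dosing:** TEAEs by relatedness and severity (6.6.1), discontinuations due to adverse events (3.5 and 6.2.4), and adherence as one minus missed doses over doses due (6.3).

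**The concern.** The reason that the SAP counts and the reason for which the protocol permits a change are different. The safety objective is to describe the safety and tolerability of somatrogon. Under Protocol 5.4.1, reducing or holding a dose is the response to a drug-related event that falls short of stopping treatment, so how often it happens is part of the tolerability description.

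If the exposure section reports only reductions attributed to IGF-I SDS >2, it may show little or nothing while other reductions and held doses go unsummarized. The comparison of the two products on this aspect would then rest on listings or on tables that the plan does not describe.

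**Working it through.** The plan states no figure on this point, so the check is a comparison of the sections and a test of what each named summary can detect.

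**Step 1. Is the counted reason a protocol trigger?**

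| | Protocol 5.4.1 | SAP 6.5.3 |
|---|---|---|
| Reason for a change | Drug-related adverse event, at discretion | IGF-1 SDS >2 |
| Type of change | Reduction, or held dose then reduction | Reduction only |

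Neither the reason nor the range of changes matches. A held dose would not enter the SAP row whatever its reason.

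**Step 2. How full can the IGF-I row be?**

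- Screening: entry requires IGF-I SDS below 2, so an eligible subject's screening value does not exceed the threshold.
- Visit 4 (Week 12): the sample is taken before the first Period II dose, as Period I treatment ends. It cannot lead to a reduction of the Period I product within Period I. It could lead to a reduction of the Period II product.
- Visit 7 (Week 24): study treatment is ending, so no later study dose remains to be reduced.
- Unscheduled values: the Schedule of Activities allows unplanned visits, and Protocol 7.2.1.2 provides for transfer of unscheduled results. A value within a period is therefore possible.

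The row is expected to be empty or nearly so, but some routes to a non-zero count remain.

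**Step 3. Do the other named summaries pick up a permitted change?**

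Take 12 weekly somatrogon doses on Days 1, 8, ..., 78 (1 + 11 × 7 = 78). Which doses are changed below is chosen for illustration only.

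*Duration, all doses given:* 78 − 1 + 7 = 84 days.

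*Severe event, dose 6 held and dose 7 reduced by 50%:*
- Duration: still 78 − 1 + 7 = 84 days.
- Amount given: 10 full doses + 0.5 = 10.5 of 12, or 87.5% of plan.
- Adherence if the held dose counts as missed: (1 − 1/12) × 100 = 91.7%.
- Adherence if the held dose is removed from the doses due: (1 − 0/11) × 100 = 100%.
- SAP 6.3 does not say which applies. Either value is above the 80% compliance threshold.

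*Moderate event, one dose reduced by 25%:*
- Duration: 84 days.
- Adherence: (1 − 0/12) × 100 = 100%.
- Amount given: 11.75 of 12, or 97.9% of plan.

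Duration detects neither change. Adherence cannot detect a reduced dose and may or may not detect a held one. TEAEs by relatedness and severity show the event but not the action taken with the dose. The discontinuation summary covers only subjects who stopped.

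**The case against.** The strongest reply has four parts.

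1. *The IGF-I row is not impossible to fill.* A reader might infer that it must be zero. The documents do not support that. Protocol 8.2.2 records an abnormal finding as an adverse event when "Test result leads to a change in study dosing (outside of any protocol-specified dose adjustments) or discontinuation from the study". A high IGF-I judged drug-related could therefore be acted on under 5.4.1, from a Visit 4 value or an unscheduled one. Section 1.3 shows that values above +2 SDS do occur. This stands.

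2. *The permitted changes may be reported after all.* A reader might infer that they appear in no output. That cannot be established. SAP 6.5.3 opens with a general commitment to summarize exposure. SAP 6.6 and 6.6.1 defer to sponsor standards (CaPS), whose content is not in the documents and may include action taken. SAP 5 puts all collected data in listings. This stands too, but a listing is not a summary, and an undescribed standard does not correct the one row that the SAP does specify.

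3. *A table specification is not a dosing rule.* A reader might infer that the sections give incompatible dosing instructions. They do not: counting reductions for one reason neither authorizes nor requires them. The mismatch is between what is permitted and what is counted.

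4. *The row carries its own qualifier, and tolerability is reported elsewhere.* This is fair. Reading an empty row as no dose reductions at all would mean ignoring the words about IGF-1. The risk of misreading is real but modest, and it is not the main reason for the change.

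**Conclusion.** The point holds in limited form. The single dose-reduction summary that the SAP names is tied to a reason absent from Protocol 5.4.1, and the reductions and held doses that 5.4.1 allows have no specified summary.

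The consequence is confined to descriptive exposure and tolerability reporting. The primary analysis, its power and its type I error do not depend on this row.

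No count of affected subjects can be given. The documents state no rate of AE-driven dose changes, and Protocol 1.3 says only that relatively few events were attributed to somatrogon in the earlier paediatric study.

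The conclusion assumes that the dosing rule in force is the one printed in Protocol 5.4.1, and that no undescribed sponsor-standard table already covers dose changes by reason. It takes no view on which dosing rule is right.

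**What to change.** Reconcile SAP 6.5.3 with Protocol 5.4.1. In the SAP, replace the IGF-I sentence with a summary of the number and percentage of subjects with any dose reduction or held dose, by treatment, period and recorded reason. Show IGF-I SDS >2 as one reason category if it was recorded. State in SAP 6.3 whether a held dose counts as missed.

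First confirm that dose changes and their reasons reach the database. Protocol 5.4.1 says that the investigator and medical monitor will communicate to track dose modifications, but the documents describe no case report form field for the change or its reason. If the sponsor-standard tables already give this breakdown, a reference to them in 6.5.3 would be enough.

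If the data are captured, the cost is one SAP sentence and one descriptive table, plus a clause in 6.3. If they are not, the reasons would have to be recovered from the tracking records. The change is to reporting only and alters no dosing instruction.
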